5. STUDY PLAN

See Schema (Table 1).

This trial is designed to evaluate the impact of ONN in addition to standard care (compared to standard care alone without ONN) on GI cancer patients' acute care utilization as well as clinical outcomes. Subjects enrolled to this study will be patients presenting to the GI clinic.

Enrollment of patients onto this study will not affect the course of their cancer treatment in any way; however, we hypothesize that those randomized to ONN will have less utilization of acute care and an improved survival compared to those receiving standard care only.

Target accrual period is anticipated to be 48 months.

5.1 Study Intervention

The study intervention is providing the patient with the service of navigation (ONN) performed under LCI Patient Navigation Program (LPNP), led by a registered oncology nurse. When the patient is diagnosed with cancer, and after successfully enrolled on the study, subject(s) who are randomized to the ONN will be assigned an ONN. Subjects can be enrolled within, but no later than, 30 days after initiation of their systemic therapy, however every effort will be made to enroll subjects prior to the initiation of systemic therapy. This ONN's first role will be to assess the subject's needs either in person at the subject's first visit, over the telephone or utilizing virtual care. The subsequent services may be continued the same way.

The ONN will aim to perform the following: expedite care, facilitate communication between the subject and providers, assist the subject in overcoming challenges throughout their treatment, ensure the subject understands their care plan, disease, and treatment, and most importantly, serve as the subject's central point of contact when questions or concerns arise.

For subject randomized for the control arm intervention will be defined as data collection only, per section 5.43.

5.2 Duration of Subject Intervention Status

Subject on intervention status will begin on the day of randomization and continue until criteria for off-intervention is met (Section 8.1).

5.3 Patient satisfaction survey

Patient satisfaction will be assessed through EORTC IL109 customized questionnaire. Subjects will be offered the option to provide patient satisfaction survey responses electronically or during a clinic visit. Completion of EORTC IL109 questionnaire can be declined by a subject at any time-point. Refusal to complete a survey will not be a protocol deviation or refrain a subject from being enrolled, and will NOT be a criterion for study discontinuation by the Investigator. If subject is not able to complete a survey during the study window, they will be asked to complete at the next scheduled in-person visit. This will NOT be considered as a protocol deviation.

5.4 Duration of Data Acquisition

Underlying primary data needed to support study endpoints will be acquired by trained study conduct research staff. For each subject, this will be done starting at the day of randomization and then on an every 3-month basis.

The duration of data acquisition will be as follows:

- For ACU, readmissions, adherence to clinical care, and subject satisfaction, the duration of data acquisition will be until the subject meets the criteria for off-intervention (see Section 8.1)
- For survival data, the duration of data acquisition will be until the subject becomes off study (see Section 8.2).

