7.2 During the Intervention

- **Subject satisfaction survey:** a EORTC IL109 customized questionnaire ([Appendix B](#)) will be collected at two time points.
1st survey at 4 weeks +2 weeks after the randomization,
2nd survey at 10-14 weeks from randomization. Patients will be provided with the option to provide survey responses electronically or during a clinic visit.

The following assessments will be performed throughout the study from the Randomization to Off-intervention every 3 months:

- **Acute Care Utilization:** unplanned inpatient admissions, emergency room encounters, and urgent care visits should be collected continuously throughout the study from the randomization.
Hospital admission and discharge dates should be tracked.
- **Adherence to clinical care:** Collect the number of visits scheduled for the subject and the number of no-shows, to include all visits scheduled within Atrium Health, not just oncology related, continuously throughout the study from the randomization.
- **Survival assessment:** Subjects will be assessed during the ONN services continuously throughout the study from the randomization.

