8. OFF INTERVENTION AND OFF STUDY

8.1 Off Intervention

Subjects will be removed from Intervention Status when at least one of the following criteria are met:

- Subject on either arm who permanently discontinues all active anti-cancer therapy
- Subject on either arm who relocates to a non-LCI institution
- Subject on either arm who relocates to an LCI site without LPNP
- Subjects randomized to the ONN arm withdraws consent to participate in the LPNP

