11.1.3 Intervention Discontinuation Date

The date when S-I becomes aware of the subject meeting any of the criteria in Section 8.1.

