11.3.2 Definition of Secondary Endpoints

- Overall Survival (OS)

OS is defined as the duration from enrollment to the study (randomization) to the date of death from any cause. Subjects who are alive or lost to follow-up at the time of the analysis will be censored at the last known date they were alive.

- Overall survival at 12 months (OS12) will be determined as a binary variable indicating whether or not the subject was alive at 12 months following randomization.

- Length of hospital stay (LOS)

Length of stay will be calculated for each subject and for each unplanned in-patient admission as the difference between the admission date and the discharge date (plus 1).

- Time from hospice referral to death

Time from hospice referral to death is defined as the duration from hospice referral to the date of death from any cause. Subjects who are alive or lost to follow-up at the time of the analysis will be censored at the last known date they were alive. This endpoint will only be calculated for subjects referred to hospice.

- 30-day readmission

The 30-day readmissions will be calculated for each subject as the total number 30-day readmissions. This endpoint will only be calculated for subjects with at least one in-patient admission.

- Referral to Supportive Oncology services

Referral to Supportive Oncology will be binary variables determined for each subject indicating whether or not the patient received referrals to Palliative Care, Nutrition Services, and Social Work Services offered by the Levine Cancer Institute Department of Supportive Oncology.

- Adherence to clinical care

Adherence to clinical care will be calculated for each subject in terms of the rate of subject compliance with scheduled visits. For each subject, the number of no-shows will be calculated as a percent of all scheduled within Atrium Health visits, regardless of visit type.

- Patient satisfaction

Patient satisfaction will be assessed through the EORTC IL109 customized questionnaire. The EORTC IL109 customized questionnaire was compiled in the EORTC web-based library system and combined selected items from the PATSAT-C33 and OUT-PATSAT7 questionnaires. The selected scales and individual items included in the IL109 questionnaire are shown in Table 11.3.2

Table 11.3.2 Scoring the IL109 customized questionnaire (Appendix B)

Scoring the PATSAT IL109	Number of items (n)	Item range*	item numbers (I1, I2, ..., In)
Scales			

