11.5.5 Secondary Analysis

Overall survival will be analyzed using Kaplan-Meier techniques. Tests of statistical significance between the arms will be carried out using the log-rank test. The 12-month survival rate will be estimated for each study arm based on the Kaplan-Meier estimates. A statistical test of significance will be carried out to compare the 12-month survival rates between the arms. This will be accomplished by pooling the standard errors of the 12-month OS rates and performing a Chi-Square test. Additional survival analyses and analysis of time from hospice referral to death will be conducted using Cox-proportional hazards models. Thirty-day readmissions will be analyzed using Poisson regression. Length of stay and adherence to clinical care will be analyzed using analysis of variance techniques. The frequencies and proportions of subjects referred to Supportive Oncology services will be calculated, alongside corresponding 95% confidence intervals estimated using the Clopper-Pearson method.

The following models will be estimated for each of the six multi-scale measures, thirteen single-item measures, and one average overall standardized score: Linear mixed models for repeated-measures will be used to analyze subject-level satisfaction as assessed through the derived endpoints of the EORTC IL109 customized questionnaire. Fixed factors included in the models will be treatment arm, sampling time (T1 and T2) and the treatment by time interaction. A random factor for subject will be included in the models to account for repeated observations on the same subject. For single-item measures, mixed-effects models for repeated ordinal outcomes will be estimated for the thirteen single-item measures using ordinal logistic regression. The response outcome may be treated as a 5-level raw score or a collapsed version (e.g., 2-level factor as raw scores 1-3 versus 4-5) as appropriate. Similarly, fixed factors included in the models will be treatment arm, sampling time (T1 and T2) and the treatment by time interaction, and a random factor for subject will be included in the models to account for repeated observations on the same subject.

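### Readmission collection stops at off-intervention, so late index stays lack a full 30-day window and this secondary endpoint is undercounted; the arm comparison is biased only if cut windows differ by arm

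*Combined protocol and SAP*

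**What the plan says.** Section 5.4 sets the end of collection: "For ACU, readmissions, adherence to clinical care, and subject satisfaction, the duration of data acquisition will be until the subject meets the criteria" for off-intervention. Section 7.2 gives the same limits ("The following assessments will be performed throughout the study from the Randomization to Off-intervention every 3 months"), and Table 2 applies them to hospital admission and discharge dates. After off-intervention only survival is followed (Sections 5.4 and 7.3).

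Two of the off-intervention triggers in Section 8.1 matter most here. One applies to both arms: "Subject on either arm who permanently discontinues all active anti-cancer therapy". The other has no control-arm counterpart: "Subjects randomized to the ONN arm withdraws consent to participate in the LPNP". Relocation out of LCI, or to an LCI site without the navigation program, is also a trigger.

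Section 11.1.3 dates discontinuation differently from Section 5.4: "The date when S-I becomes aware of the subject meeting any of the criteria in Section 8.1".

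Section 11.3.2 defines the endpoint as a raw total: "The 30-day readmissions will be calculated for each subject as the total number 30-day readmissions". On who is counted it says: "This endpoint will only be calculated for subjects with at least one in-patient admission". Section 11.5.5 adds: "Thirty-day readmissions will be analyzed using Poisson regression". No section requires a complete 30-day window, says what to do with an incomplete one, or names an offset.

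**The concern.** A 30-day readmission can be observed only if the subject is watched for 30 days after discharge. Here the watch ends at an event, the end of therapy, that can easily fall during or soon after a hospital stay. A readmission after that point is not collected, but the subject stays in the analysis and the discharge contributes zero.

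Two things are at stake. The first is the absolute readmission rate, which is too low in any arm with such stays. The second is the comparison between arms. If navigation changes when therapy ends, or if withdrawals from the navigation program end collection in the ONN arm only, the arms could have different shares of cut windows. A ratio away from 1 could then appear with equal true risk, in either direction.

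**Working it through.** The documents give no readmission rate, power or sample size for this endpoint, so there is no planned figure to reproduce. The size below is an illustration.

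**Inputs from the documents:** end of collection (5.4, 7.2, Table 2), triggers (8.1), raw count in admitted subjects (11.3.2), Poisson regression without a named offset (11.5.5).

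**Assumed inputs:** true 30-day readmission rate r = 25%; readmission times uniform over the 30 days; time to therapy stop after discharge exponential with median 6 months (182.6 days); p = share of index stays at which therapy stops, leaving a zero-day window.

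**Undercount.** The daily hazard of therapy stop is h = ln 2 / 182.6 = 0.0038, so 30h = 0.114. The mean fraction of the window still observed is m = (1 − e^(−30h)) / (30h) = (1 − 0.892) / 0.114 = 0.945. The observed rate is r × (1 − p) × m.

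- p = 0: 0.25 × 0.945 = 23.6%, so 5.5% of readmissions are missed.
- p = 10%: 0.25 × 0.90 × 0.945 = 21.3%.
- p = 20%: 0.25 × 0.80 × 0.945 = 18.9%, so 24% are missed. Incomplete windows: 1 − 0.80 × 0.892 = 28.6%.
- p = 40%: 0.25 × 0.60 × 0.945 = 14.2%.

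Most of the loss in the higher figures comes from p, not from therapy stops after discharge.

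**A milder model.** Let s be the share of index discharges with a cut window. If the cut falls uniformly within the 30 days, the captured fraction is 1 − s/2; if all cut windows are zero-day, it is 1 − s. For s = 20% the loss is 10% or 20%.

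**Arm ratio with no true difference** (arm with fewer cuts over arm with more):

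- Equal shares, 30% and 30%: 1.00 under either model.
- 15% against 30%: 0.925 / 0.85 = 1.09 with a uniform cut; 0.85 / 0.70 = 1.21 with zero-day windows.
- No stop at the index stay, and only the median time to therapy stop differs: 9 against 6 months gives 0.963 / 0.945 = 1.02; 8 against 4 months gives 0.959 / 0.919 = 1.04.

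These are ratios per discharge. The planned analysis uses a total per subject, so its ratio also depends on discharges per subject.

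**The case against.** Counting events while on intervention is a coherent choice, applied by the same section to acute care use and adherence in both arms. On that view only a censoring sentence is missing. That stands in part: the cutoff is not wrong in itself, but a fixed 30-day count without a window rule does not fit it.

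Three stronger readings are tempting, and the documents do not support them.

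- *The plan counts cut windows as no readmission.* It does not say so. This follows by default from a raw total.
- *The arm comparison is biased.* No share of cut windows is given for either arm, and equal shares give a ratio of 1.00. The ONN-only withdrawal trigger and a possible effect of navigation on when therapy ends make a difference possible, not shown.
- *The data cannot be repaired.* Hospital dates on intervention and the discontinuation date are recorded, so cut windows can be identified and then censored or excluded. Later abstraction for subjects still on study is not ruled out either. What the plan does not provide is the readmissions after the stop.

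Zero-day windows are also a worst case. If the awareness date in Section 11.1.3 governs, with data gathered every 3 months, some windows lengthen. None is guaranteed to reach 30 days, and Section 5.4 points to the date the criterion is met. The illustration also ignores death and hospice care after therapy ends, which would change the true readmission rate in that period.

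**Conclusion.** The point holds as an undercount of a secondary endpoint. Followed as written, the plan misses any readmission that falls within 30 days of discharge but after off-intervention, and keeps the subject in the count. The direction is certain wherever this occurs; the size is not known. On the assumed 25% rate and 6-month median, it runs from about 5.5% of readmissions missed, if no therapy stop coincides with an index stay, to about 24% if therapy stops at 20% of stays with zero-day windows.

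A spurious arm difference is conditional on unequal shares of cut windows. A 15% against 30% split, which has no basis in the documents, would give a ratio of about 1.09 to 1.21. The 6-month survival co-primary is not affected, because survival is followed until off study. The change is worth making because it is cheap and because the post-stop readmissions are otherwise not collected.

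**What to change.** - **Sections 5.4, 7.2 and Table 2:** for every unplanned admission that begins on intervention, collect the discharge date and any readmission through 30 days after discharge, regardless of off-intervention, for subjects still on study. The rule should attach to the start of the admission. A rule limited to discharges on intervention would omit stays during which therapy is stopped, which drive most of the worst-case loss.
- **Sections 5.4 and 11.1.3:** state whether collection ends on the date the criterion is met or the date of awareness.
- **Section 11.3.2:** let the window end early only at death, off study or loss of record access, for example relocation to a non-LCI institution.
- **Section 11.5.5:** use the log of observed post-discharge days within the 30-day windows as the Poisson offset. This assumes a constant hazard over the window, and a zero-day window adds no information, so it supports the extended collection and does not replace it.
- **Reporting:** give the number of cut windows and of deaths within 30 days of discharge, by arm.

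The cost is up to 30 more days of record abstraction for a subset of subjects, plus protocol wording. Capture will stay incomplete for those who relocate, since their records may be out of reach and routine contact after off-intervention is for survival only, about every 6 months.

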6. STUDY CALENDAR

Table 2. Study Procedures and assessments

Study Procedures	Registration	Baseline ²	During the Intervention ⁸	Off-intervention ⁹	Survival Follow-up
Informed Consent	X				
Demographics¹		X			
Medical History³		X			
Adherence to clinical care⁴			Continuously throughout the study from Randomization to Off-intervention every 3 months¹¹		
Acute Care Utilization⁵					
Collection of subject's hospital admission and discharge dates⁶					
Survival assessment			X¹⁰		
Subject satisfaction survey			X ⁷	X ⁷	

Key to Footnotes

¹ Demographic information will include: DOB, sex, race, live-in caregiver status, income, insurance status, education level, zip code.

² Screening window is at most 28 days prior to enrollment.

³ The following baseline medical history information will be manually collected from EMR: smoker status, diabetes, ETOH use, BMI, weight, clinically significant pre-existing conditions, and treatment and procedure history.

⁴ Collect the number of visits scheduled for the subject and the number of no-shows, to include all visits scheduled within Atrium Health, not just oncology related.

⁵ Collect unplanned inpatient hospital admissions, emergency room encounters, and urgent care visits.

⁶ Hospitalization encounter is temporally defined as a difference between date of discharge and subtracted date of admission.

⁷ Assessed by a EORTC IL109 customized questionnaire ([Appendix B](#)). It will be collected in two time points. 1st survey will be collected at 4 weeks +2 weeks after the randomization, 2nd survey at 10-14 weeks from the randomization. Subjects will be offered the option to provide survey responses electronically or during a clinic visit. If subject is not able to complete a survey during the study window, they will be asked to complete at the next scheduled in-person visit. This will NOT be considered as a protocol deviation.

⁸ If subject remains on study after the relocation from one LCI site to another LCI site, subject will remain on their original arm he/she was randomized to.

⁹ Subject will become off-intervention and enter the survival follow-up after meeting the criteria for off-intervention, [Section 8.1](#).

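### Satisfaction surveys stop at off-intervention under Section 5.4 but are also marked under Off-intervention in Table 2, and late forms have no last day or rule assigning them to T1 or T2

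*Combined protocol and SAP*

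**What the plan says.** Section 5.4 groups satisfaction with acute care utilization, readmissions and adherence: "and subject satisfaction, the duration of data acquisition will be until the subject meets the criteria for off-intervention". Section 7.2 places the survey under the intervention period, and Section 7.3 lists only survival after it.

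In Table 2 (Section 6), the row "Subject satisfaction survey" carries a mark with footnote 7 under During the Intervention and another under Off-intervention, and none under Survival Follow-up. Footnote 7 gives two time points only: "1st survey will be collected at 4 weeks +2 weeks after the randomization, 2nd survey at 10-14 weeks from the randomization". Footnote 9 explains the status: "Subject will become off-intervention and enter the survival follow-up after meeting the criteria for off-intervention".

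For late forms, Section 5.3 (repeated in footnote 7) says: "If subject is not able to complete a survey during the study window, they will be asked to complete at the next scheduled in-person visit". It adds: "This will NOT be considered as a protocol deviation".

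Section 11.5.5 analyzes the scores with mixed models for repeated measures: "Fixed factors included in the models will be treatment arm, sampling time (T1 and T2) and the treatment by time interaction". The missing-data rules in Section 11.3.2 cover unanswered items within a form. They do not cover a form that is wholly missing or out of window.

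**The concern.** There are two separate problems, both affecting the second survey.

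The first is who receives it. A subject can leave intervention status before week 10 and remain on study, and the texts then give a site two different instructions. Under 5.4 the T2 form is not collected. One of the four off-intervention criteria in Section 8.1, withdrawal of consent to LPNP, exists only in the ONN arm and is plausibly connected with how satisfied the subject is. Missing T2 forms may therefore differ between arms and depend on the outcome being measured.

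The second is what the label T1 means. A late T1 form has no latest date, so it may be completed when T2 is due. Two forms filled in at about the same time would then enter the model as two different times, which weakens the time and arm-by-time terms.

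**Working it through.** The plan gives no figure on this point to reproduce. The check sets the provisions side by side and adds calendar arithmetic.

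**1. Which text governs after off-intervention**

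| Place | Survey after off-intervention? |
|---|---|
| Section 5.4 | No; collection ends when Section 8.1 is met |
| Sections 7.2 and 7.3 | No; the survey is listed during the intervention, survival only afterwards |
| Table 2, Off-intervention column (as extracted) | Yes |
| Footnote 7 | Silent on status; both surveys counted from randomization, no exit survey |

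Take a subject who goes off intervention at week 7. T2 falls due at weeks 10-14. Section 5.4 gives no T2 form, while Table 2 allows one.

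**2. Whether such subjects stay in the analysis.** Under Section 8.2 only off-study status ends all data collection; off-intervention subjects pass to survival follow-up. If they had at least one dose of systemic therapy on or after enrollment, and either died within 6 months or stayed on study for 6 months, they are in the evaluable population (Section 11.4) used for this endpoint.

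**3. Which arms are affected.** Three of the four criteria in Section 8.1 apply to both arms: stopping all anti-cancer therapy, moving to a non-LCI institution, and moving to an LCI site without LPNP. The fourth, withdrawing from LPNP, applies to the ONN arm only.

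**4. How many could be affected (illustration).** The documents give no time to off-intervention. Assume it is exponential, so the share off intervention by time t is 1 − 0.5^(t/median). One month is 365.25/12/7 = 4.348 weeks, so week 10 is 2.30 months and week 14 is 3.22 months.

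| Assumed median | By week 10 | By week 14 |
|---|---|---|
| 4 months | 33% | 43% |
| 6 months | 23% | 31% |
| 8 months | 18% | 24% |
| 12 months | 12% | 17% |

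With 150 per arm, the week-10 column runs from 150 × 0.124 ≈ 19 to 150 × 0.329 ≈ 49 subjects per arm. These counts ignore deaths, refusals and subjects no longer treated at LCI, so the number of recoverable forms would be smaller.

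**5. When a late T1 reaches the T2 window.** T1 closes at week 6 and T2 opens at week 10, a gap of 10 − 6 = 4 weeks. Overlap therefore needs the next in-person visit to be at least 4 weeks after week 6. If that visit is uniformly spread over a visit interval of k weeks (assumption), the chance that it falls at week 10 or later is max(0, (k − 4)/k):

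- k up to 4 weeks: 0%
- k = 6 weeks: 2/6 = 33%
- k = 8 weeks: 4/8 = 50%

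The research contact every 3 months ± 2 weeks (footnote 11) falls at 13.0 ± 2, about weeks 11.0 to 15.0. That is mostly inside the T2 window, so a T1 form completed at a clinic visit then would coincide with T2.

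**The case against.** The prose of 5.4, 7.2 and 7.3 is consistent, and the contradiction rests on one table cell whose column position comes from extracted text. The survival row of the same table shows a single mark although footnote 10 requires survival assessment after off-intervention too, so the layout may not be reliable. The two survey marks might simply stand for the two time points, or the second might mean a form at the moment of leaving. This limits how firmly the contradiction can be stated. It does not remove the loss of T2: if the cell is an artefact, 5.4 stands unopposed and T2 is still dropped for subjects who remain on study.

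Stopping can also be defended from the instrument. Appendix B asks for answers only from people currently in outpatient care and rates the hospital giving it. That has force for subjects who leave LCI, but it argues for restricting by outpatient status, not intervention status. A subject who withdraws from LPNP, or moves to an LCI site without it, may still be an LCI outpatient.

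The mixed models keep a leaver's T1 score, which softens the loss. They do so under a missing-at-random assumption, which is doubtful when leaving is tied to stopping therapy or rejecting navigation. Subjects may also decline any survey, so not every form would be recovered.

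On late forms, the next scheduled in-person visit is a bound of a kind, and electronic completion should reduce missed T1 forms. The questionnaire covers the whole course of illness, so a short delay matters less. For the same reason, two forms completed together would carry little information about change.

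**Conclusion.** The point holds as a low-cost correction to a secondary endpoint; neither co-primary endpoint is touched. Section 5.4 and Table 2 need reconciling. Section 5.4 as written drops T2 for on-study subjects in both arms, through one route that exists only in the ONN arm. The late-form rule has no last day and no assignment to T1 or T2.

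Three stronger readings are tempting and are not supported:

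- A reader might infer a bias toward ONN of about 1.0 to 1.5 points on the 0-100 scale: if 5% of ONN subjects withdrew and would have scored 20 to 30 points lower, 0.05 × 20 = 1.0 and 0.05 × 30 = 1.5. Neither input is in the documents, the sum is complete-case arithmetic while the planned models retain T1, and control subjects lose T2 as well. The size and net direction are unknown.
- A reader might infer that only subjects who leave navigation are affected. Three of the four criteria apply to either arm.
- A reader might infer that T1 forms will commonly be completed at T2. This needs a visit gap of at least 4 weeks after week 6, so it is unlikely with visits every 2-3 weeks. The documents give no visit interval for subjects on therapy.

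**What to change.** 1. Remove satisfaction from the off-intervention bullet in Section 5.4. Align Sections 7.2 and 7.3 and Table 2 so that both surveys are requested at weeks 4-6 and 10-14 from randomization whatever the intervention status, for subjects who are alive, on study and still receiving outpatient care at LCI. This matches the Appendix B instruction. Use the electronic option already offered.
2. In Section 5.3 and footnote 7, and in the analysis dataset, assign forms by actual completion date: T1 before week 10, T2 from week 10 to a last day that the sponsor states.
3. If T1 has not been completed before week 10, give only T2.

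The cost is wording in Sections 5.3, 5.4, 7.2 and 7.3, Table 2 and footnote 7, plus one date rule; no visit is added. A few late forms are given up. Collection changes partway through the trial, since interim analyses have already taken place, and T2 forms missed before the amendment cannot be recovered.

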11.3 Endpoints

11.3.1 Definition of Primary Endpoints

Overall survival at 6 months (OS6) will be determined as a binary variable indicating whether or not the subject was alive at 6 months following randomization.

Acute care utilization visits will be calculated for each subject as the total number of acute care visits normalized to an annual basis. Acute care visits will include unplanned hospital admissions, ED visits, and urgent care visits.

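### The co-primary acute care count stops at off-intervention, an event that can differ by arm and has one criterion that only navigated subjects can meet, so the comparison can be biased in either direction

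*Combined protocol and SAP*

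**What the plan says.** Section 5.4 sets two follow-up windows. For ACU, readmissions, adherence and satisfaction, "the duration of data acquisition will be until the subject meets the criteria for off-intervention". By contrast, "For survival data, the duration of data acquisition will be until the subject becomes off study". The ACU window is repeated in the study calendar (Section 6, Table 2) and in Section 7.2 ("throughout the study from the Randomization to Off-intervention every 3 months"), so it is the operative rule and not a slip.

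Section 8.1 lists four off-intervention criteria. Three apply to both arms: the end of treatment ("Subject on either arm who permanently discontinues all active anti-cancer therapy"), a move to a non-LCI institution, and a move to an LCI site without the navigation program. The fourth applies to one arm: "Subjects randomized to the ONN arm withdraws consent to participate in the LPNP". Section 11.1.3 dates intervention discontinuation as "The date when S-I becomes aware of the subject meeting any of the criteria in Section 8.1", which need not be the day of the event.

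Section 11.3.1 defines the endpoint for each subject as "the total number of acute care visits normalized to an annual basis". Section 11.5.4 compares the arms by Poisson regression with arm as the primary covariate. No section provides for visits after off-intervention, a common counting window, or a sensitivity analysis for unequal stopping.

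**The concern.** Randomization protects a comparison when both arms are observed over periods that the arm does not determine. Here observation ends on a post-randomization event. A subject who leaves the navigation program stops contributing visits; a control subject in the same clinical state keeps being counted. Permanent discontinuation of anti-cancer therapy applies to both arms, but navigation may shift its timing either way.

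If use of acute care rises as illness advances, the point where counting stops decides how much of the high-use period enters the rate. The ACU test could then show a difference when acute care use does not differ, or hide a true one. The design effect is a 20% reduction, so a bias of a few percent matters and one of 10 to 20% would dominate the result.

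**Working it through.** **1. The plan's own figure.** Section 11.2 claims at least 93% power for a fall from 6 to 4.8 visits per year at two-sided alpha 0.025. Use power = Φ(|ln 0.8| / SE − z), with SE = √[(1/6 + 1/4.8)/(n·t)], z = 2.2414 and t = 1 year of counting per subject.
- n = 107 per arm (before the sample size re-estimation): SE = 0.0592, 0.2231/0.0592 = 3.77, power 93.7%.
- n = 150 per arm: SE = 0.0500, power 98.7%.

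The claim holds as a lower bound. It rests on a full year per subject and says nothing about who stops being counted, or when.

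**2. Whether other parts of the plan repair the stopping rule.**
- The evaluable population (Section 11.4) requires death within six months or six months on study, not on intervention. An ONN subject who leaves LPNP early stays in the analysis with a truncated count.
- The intervention-compliant population asks for one LPNP encounter within two weeks of randomization, so later withdrawal does not affect it.
- Annualizing corrects unequal duration only if a subject's visit rate is constant over time.

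**3. Hand examples.** There is no true effect and 150 subjects per arm. The visit patterns are assumptions, because the documents give none. The chance of a false finding in one direction is Φ(−2.2414 + |ln RR|/SE), which is 1.25% without bias.

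*LPNP withdrawal at the start of deterioration.* Every subject has 9 months at 5 visits/year, then 3 months at 15/year.
- Control: 5×0.75 + 15×0.25 = 7.5 visits in 1 year.
- ONN with 10% withdrawing at month 9: visits 0.9×7.5 + 0.1×3.75 = 7.125; time 0.9 + 0.1×0.75 = 0.975 year; rate 7.308; ratio 0.974. SE = √[1/(150×7.5) + 1/(150×7.125)] = 0.0427; false finding for ONN 5.1%.
- With 5% withdrawing: ratio 0.987, false finding 2.6%. With a late rate of 10/year instead of 15: ratio 0.992, false finding 1.9%.
- Averaging annualized rates per subject does not help: 0.9×7.5 + 0.1×5 = 7.25, ratio 0.967.

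*Low users leave.* The overall rate is 6/year, and 10% of ONN subjects, with 3/year, leave at month 3. The others have (6 − 0.3)/0.9 = 6.333. Visits 5.7 + 0.075 = 5.775; time 0.925; rate 6.243; ratio 1.041, against ONN. This case needs person-time weighting; equal weighting of annualized rates removes it.

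*Therapy ends at different times.* Subjects have 5/year for 9 months, then 12/year. Controls are counted 2 months into the late phase: 3.75 + 2 = 5.75 visits in 11/12 year = 6.273/year. If 25% of ONN subjects stop at month 9: visits 0.75×5.75 + 0.25×3.75 = 5.25; time 0.75×0.9167 + 0.25×0.75 = 0.875; rate 6.00; ratio 0.957, false finding for ONN 9.0%. With the arms exchanged the ratio is 1.045, with the same 9.0% against ONN.

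**4. Simulation with the plan's survival assumption.** 400,000 exponential survival times with an 8-month median (Section 11.2) in both arms. Assumed: visit rate 2 to 4 times higher in the last 2 to 3 months of life; control counting ends 0.5 to 1 month before death; counting capped at 12 months (without the cap the ranges agree to two decimals). Rate = visits/person-time, so the base rate cancels. False-finding chances use an assumed SE of the log rate ratio of 0.07 to 0.10.

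| Shift in ONN counting | Spurious rate ratio | False finding |
|---|---|---|
| 10% stop 1 month earlier | 0.982-0.994 | 1.5-2.4% for ONN |
| 25% stop 1 month earlier | 0.953-0.986 | about 2-6% for ONN |
| All stop 0.5 month earlier | 0.902-0.970 | about 3-22% for ONN |
| All stop 1 month earlier | 0.801-0.939 | about 5-83% for ONN |
| All counted 0.5 month longer | 1.029-1.093 | about 3-17% against ONN |

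**The case against.** The strongest counter-argument concerns direction. A reader might infer that the rule favors ONN, because navigation and its referrals could bring forward the end of therapy. The documents do not support that. The synopsis and Section 5 say enrollment will not alter the course of cancer treatment, and Section 1.1.6 describes navigators as helping patients complete it. On that text ONN could as easily prolong therapy, extend counting into high-use time and bias the result against itself. Palliative care and hospice referral are secondary outcomes, so earlier stopping is possible, but no section expects it.

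Size is the second objection. The documents give no LPNP withdrawal rate, no therapy duration by arm and no visit rate by phase of illness. Ratios near 0.80 need every ONN subject to be shifted by a month. The one asymmetry that is certain from the text, LPNP withdrawal, has little effect at about 5% withdrawal (ratios 0.987-0.992 in the examples). The other three criteria apply to both arms.

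Both objections stand as limits on direction and size. Neither removes the defect: the rule lets observation time depend on arm, and nothing in the analysis corrects stopping that is related to the visit rate. An on-treatment question, had one been stated, would not justify a stopping criterion that exists in one arm only.

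**Conclusion.** The concern holds as a risk of bias in either direction to a co-primary comparison. The text establishes that counting ends at a post-randomization event and that one of its criteria is confined to ONN. It does not establish that the windows will in fact differ, which way, or by how much. Under the stated assumptions the bias is about 1-2% if a tenth of ONN subjects stop a month earlier, 1-5% if a quarter do, and reaches the whole 20% design effect only at the extreme where all do. The opposite shift of half a month in all ONN subjects gives 3-9% against ONN. The rule should be corrected before the primary analysis, because the bias cannot be estimated afterwards if later visits were never collected.

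**What to change.** In Sections 5.4, 6, 7.2 and 11.3.1:

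- State that withdrawal from LPNP does not end ACU collection in the ONN arm. This is consent to the program, not to the study, and Section 8.2 treats withdrawal of study consent separately.
- Define the primary ACU count in both arms over the same window from randomization, to death, off study or a prespecified common cutoff, regardless of off-intervention status. The choice of cutoff is the sponsor's; the documents do not imply a particular one.
- Keep the on-intervention count as a sensitivity analysis, and state which date closes its window, since Section 11.1.3 uses the date of awareness.
- Specify log time at risk as the offset in the Poisson model.

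Section 1.1.7 describes navigation of advanced patients to the end of life, while Section 8.1 ends intervention status when therapy ends. These passages should be reconciled.

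The cost is an amendment and extra record abstraction for off-intervention subjects, partly retrospective because interim analyses have already taken place. Abstraction is already in use (Section 10.1.1), but off-intervention contact is best-effort, about every 6 months, and for survival only. Subjects who move outside the health system would be censored at the move. Death remains a post-randomization end of counting that ONN is hypothesized to affect, so the change reduces the problem without removing it.
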